[name]
[contact]
[contact]

Bioanalytical Laboratory
Celerion
[name]
[name]
Contact: [name]
[contact]

SYNOPSIS

Study Objectives	
Primary:
 
 1. To evaluate and compare the maximum plasma concentration (C_{max}) and the area under the concentration-time curve at the last time point measured (AUC_t) of nicotine after the use of each Heated Tobacco product or cigarette comparator. 
Secondary:
 
 1. To evaluate other pharmacokinetic (PK) parameters of nicotine after the use of each Heated Tobacco product or cigarette comparator. 2. To evaluate the reduction in smoking urges observed after the use of each Heated Tobacco product or cigarette comparator. 3. To evaluate product perception and preference by use of subjective assessments. 4. To evaluate the tolerability and safety of each of the products used. 5. To investigate usage behaviour for each product using measurements of topography parameters (puff count, puff duration, puff volume, peak puff flow rate, average puff flow rate, inter puff interval) for each product.

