- o: Subjects will be familiarised with the questionnaires. An explanation of how the questionnaires will be administered to the subjects will be given. Responses will not be recorded.
- p: To be performed approximately 10 minutes prior to the start of the product use session.
- q: To be performed approximately 30 seconds prior the scheduled PK blood draws.
- r: On Day -1, subjects will participate in a Product Trial period where subjects will consume one HT stick (flavour chosen by subject).
- s: On Days 3 and 4 only, puff topography measurements will be performed for 2 hours during the last 2 hours of the 4-hour *ad libitum* product use session. The topography session will span a 2-hour period and the SPA-M topography device will be stopped and restarted with each new stick or cigarette during that time.
- t: The CRU will attempt to contact all subjects who used at least one study product (including subjects who terminate the study early) using their standard procedures approximately 7 days after the final product use to determine if any AE has occurred since the last study visit.

Abbreviations: AE = Adverse event, BMI = Body mass index, BP = Blood pressure, Chem = Serum chemistry, CO = Carbon monoxide, CRU = Clinical research unit, ECG = Electrocardiogram, EOS = End-of-study, FSH = Follicle-stimulating hormone, FU = Follow-up, HBsAg = Hepatitis B surface antigen, HCV = Hepatitis C virus, HIV = Human immunodeficiency virus, HR = Heart rate, HT = Heated tobacco, I/E = Inclusion/exclusion, IP = Investigational product, PK = Pharmacokinetic(s), RR = Respiratory rate, Scr = Screening, SPA-M = Sodim Smoking Puff Analyzer Mobile, T = Temperature, OBCC = Own brand combustible cigarette.

ABBREVIATIONS

AE	Adverse event
ANOVA	Analysis of variance
AUC	Area under the concentration-time curve
AUC ₀₋₉₀	Area under the nicotine concentration-time curve from time 0 to 90 minutes
AUC ₀₋₂₄₀	Area under the nicotine concentration-time curve from time 0 to 240 minutes
AUC _{inf}	Area under the nicotine concentration-time curve from time 0 to infinity
AUC _t	The area under the concentration time curve, from time 0 to the last observed non-zero concentration, as calculated by the linear trapezoidal method.
AUEC ₀₋₂₄₀	Area under the change from baseline score versus time curve from time 0 to 240 minutes
BMI	Body mass index
BP	Blood pressure
bpm	Beats per minute
°C	Degree Celsius
CC	Combustible cigarette
CFR	Code of Federal Regulations
CI	Confidence interval

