C _{last}	Plasma concentration at last time point
C _{max}	Maximum measured plasma concentration
CO	Carbon monoxide
CPD	Cigarette(s) per day
CRF	Case report form
CRU	Clinical research unit
EC	Ethics committee
ECG	Electrocardiogram
E _{max}	Maximum change from baseline score
EOS	End-of-Study
°F	Degree Fahrenheit

FDA	Food and Drug Administration
FSH	Follicle-stimulating hormone
g	Gram
GCP	Good Clinical Practice
HIV	Human immunodeficiency virus
HR	Heart rate
HT	Heated tobacco
HTP	Heated tobacco product
ICF	Informed consent form
ICH	International Council for Harmonisation
ITU	Intent to Use
K ₂ -EDTA	Dipotassium ethylenediaminetetraacetic acid
kg	Kilogram
ln	Natural logarithm
m ²	Meters squared
mAh	Milliampere hour
mg	Milligram
mL	Milliliter
mmHg	Millimeter of mercury
ng	Nanogram
NGP	Next generation product(s)
OBCC	Own brand combustible cigarette
PK	Pharmacokinetic(s)
ppm	Parts per million
PPS	Product Preference Scale
QA	Quality Assurance
RCF	Relative centrifugal force
REC	Research Ethics Committee
SAE	Serious adverse event
SAP	Statistical analysis plan
SOP	Standard operating procedure
SPA-M	Sodim Smoking Puff Analyzer Mobile

SUSAR	Suspected unexpected serious adverse reaction
TE _{max}	Time of the Emax
T _{max}	Time to reach the maximum measured plasma concentration
US or USA	United States of America
USB	Universal serial bus
V	Volt
VAS	Visual analog scale

DEFINITION OF TERMS

Check-in	Check-in is defined as the time when the subject arrives at the CRU to start confinement
Concomitant medication	Concomitant medication refers to all medication taken during the study conduct period from 28 days prior to Screening through End-of-Study. Medications started prior to Screening but which the subject continues to take during the study, are considered to be concomitant medications
Randomisation	Assignment of subjects to a specific sequence
Screening	Screening is defined as the 27-day period prior to study procedures on Day -1, during which subjects will undergo screening assessments
Screening failure	Any subject who does not meet the entry criteria at Screening or Day -1 for study enrollment will be considered a Screening failure
Sponsor	‘Sponsor’ refers to Imperial Brands PLC
Subject	‘Subject’ refers to an individual who participates in the clinical study

TABLE OF CONTENTS

PROTOCOL REVISION HISTORY	2
SPONSOR SIGNATURE PAGE	6
PRINCIPAL INVESTIGATOR SIGNATURE PAGE	7
STUDY CONTACTS	8
SYNOPSIS	9
STUDY EVENTS FLOW CHART	14
ABBREVIATIONS	17
DEFINITION OF TERMS	20

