8.3 Pharmacokinetic Concentrations

For the concentration tables, unadjusted plasma nicotine concentrations that are BLQ will be set to one-half of the lower limit of quantitation for the calculation of descriptive statistics.

Individual nicotine concentrations will be adjusted for baseline nicotine (“baseline-adjusted”) and all PK parameters will be calculated based on the adjusted concentrations. Baseline adjustment will be performed by subtraction of the pre-existing nicotine concentration from each nicotine concentration obtained after test product administration in that period/day for each subject using the following equation:

$$C_t = C_{t \text{ unadjusted}} - [C_0 \cdot e^{-K_{el} \cdot t_1}]$$

where C_t is the adjusted concentration at time t , $C_{t \text{ unadjusted}}$ is the observed concentration at time t , C_0 is the pre-product use concentration (-5 minutes), $K_{el} = \frac{\ln(2)}{t_{1/2}}$, $t_{1/2}$ is 2 hours (average nicotine half-life), t is the actual sampling time since product administration, and t_1 is the actual sampling time since the time of the pre-product use sample.

After correction for pre-product administration values, some concentrations may be below the limit of quantitation (BLQ) and some may be negative values. Negative values will be assigned a value of zero in the analyses and all other values obtained will be reported as is even if these values are BLQ.

Baseline-adjusted plasma nicotine concentrations will be used for the calculation of the plasma nicotine PK parameters.

Imperial Brands PLC
 Project No. NER01/0004
 Celerion Project No. CA35183

All concentration data will be included in the calculation of the individual PK parameters, the individual concentration-time plots (based on actual sample times), and in the mean concentration-time plots (based on nominal sample times). However, if there are any significant deviations from nominal sample times, some concentration data may be excluded from the descriptive statistics and the mean concentration-time plots and/or additional concentration-time plots of the mean data may be provided. All deviations and excluded data will be listed and discussed in the CSR.

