8.4 Noncompartmental Pharmacokinetic Analysis and Parameter Calculation

The appropriate noncompartmental PK parameters will be calculated from the baseline-adjusted plasma nicotine concentration-time data using Phoenix® WinNonlin® Version 8.1 or higher. Actual sample times will be used in the calculations of the PK parameters. The calculation of the actual time for plasma nicotine will be in respect to the start of product use. All PK parameters included in the protocol are listed in [Table 8.1](#) below, and are defined as appropriate for study design.

Table 8.1. Noncompartmental Pharmacokinetic Parameters to be Calculated

Parameter	Label to be Used in the Text, Tables and Figures	Definition	Method of Determination
AUC ₀₋₉₀	AUC0-90	
Area under the baseline-adjusted nicotine concentration-time curve from time zero (defined as the start of the product use session) to the 90-minutes time point.
 
If the 90-minutes plasma concentration is missing, BLQ, or not reportable, then interpolation and/or extrapolation will be conducted, as appropriate. If interpolation and/or extrapolation cannot be reliably performed, then this parameter cannot be calculated.
	Calculated using the Linear Trapezoidal with Linear Interpolation Method

Imperial Brands PLC
 Project No. NER01/0004
 Celerion Project No. CA35183

Parameter	Label to be Used in the Text, Tables and Figures	Definition	Method of Determination
AUC ₀₋₂₄₀	AUC0-240	
Area under the baseline-adjusted nicotine concentration-time curve from time zero (defined as the start of the product use session) to the 240-minutes time point.
 
If the 240-minutes plasma concentration is missing, BLQ, or not reportable, then interpolation and/or extrapolation will be conducted, as appropriate. If interpolation and/or extrapolation cannot be reliably performed, then this parameter cannot be calculated.
	Calculated using the Linear Trapezoidal with Linear Interpolation Method
AUC _t	AU Ct	Area under the baseline-adjusted nicotine concentration-time curve from time zero (defined as the start of the product use session) to the time of the last measurable non-zero concentration.	Calculated using the Linear Trapezoidal with Linear Interpolation Method
AUC _{inf}	AUCinf	Area under the baseline-adjusted concentration-time curve from time 0 extrapolated to infinity	Calculated as: AUC _t + (C _{last} /K _{el}) where C _{last} is the last observed/measured concentration

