AUC% _{extrap}	AUC% _{extrap}	Percent of AUC _{inf} extrapolated to infinity	Calculated as: (1 – AUC _t /AUC _{inf}) x 100
C _{max}	Cmax	Maximum baseline-adjusted plasma concentration over the duration of the measurement interval.	Taken directly from bioanalytical data
C _{last}	Clast	Plasma baseline-adjusted nicotine concentration at last time point measured.	Taken directly from bioanalytical data
T _{max}	T _{max}	Time to reach the maximum baseline-adjusted plasma concentration. If the maximum value occurs at more than one time point, T _{max} is defined as the first time point with this value	Taken from clinical database as the difference in the time of administration and the time of the blood draw which is associated with the C _{max}

Imperial Brands PLC
 Project No. NER01/0004
 Celerion Project No. CA35183

Parameter	Label to be Used in the Text, Tables and Figures	Definition	Method of Determination
$T_{1/2}$	$T_{1/2}$	Apparent first-order terminal elimination half-life.	Calculated as $\ln 2/K_{el}$
K_{el}	K_{el}	Apparent first-order terminal elimination rate constant	Calculated by linear least-squares regression analysis using the maximum number of points in the terminal log-linear period (e.g., three or more non-zero plasma concentrations).

Pharmacokinetic parameters will not be calculated for subjects with less than 3 consecutive post-product administration time points with quantifiable concentrations. Subjects for whom there are insufficient data to calculate the PK parameters will be included in the concentration tables only and excluded from the summary statistics, statistical analysis, and mean profiles.

The K_{el} will be determined using linear regressions composed of least 3 data points. The K_{el} will not be calculated if 1) the terminal elimination phase is not apparent, 2) if C_{max} is one of the 3 last data points, or 3) if the R^2 value is less than 0.75. In cases where the K_{el} interval is not calculated, the values of $T_{1/2}$ will not be reported.

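### Clast is taken at the last time point but AUCt stops at the last non-zero value, so a zeroed 240-minute concentration leaves AUCinf with no tail and below AUC0-240

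*Protocol*

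**What the plan says.** **Clast.** The protocol abbreviation is "Plasma concentration at last time point". Protocol 7.3.1 and SAP Table 8.1 (Section 8.4) both have "Plasma baseline-adjusted nicotine concentration at last time point measured". None of the three requires a non-zero value.

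**AUCt.** The protocol abbreviation runs "from time 0 to the last observed non-zero concentration, as calculated by the linear trapezoidal method". SAP Table 8.1 runs "to the time of the last measurable non-zero concentration". Protocol 7.3.1 gives only an undefined time t. The synopsis primary objective describes AUCt as "the area under the concentration-time curve at the last time point measured". The objectives in Protocol 2.1 and SAP 2.1 give no end point.

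**AUCinf and AUC%extrap.** SAP Table 8.1 sets AUCinf = AUCt + Clast/Kel and adds that Clast "is the last observed/measured concentration". AUC%extrap = (1 − AUCt/AUCinf) × 100.

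**Zeros.** SAP 8.3: "Negative values will be assigned a value of zero in the analyses". Protocol 7.3.1 has the same rule.

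**AUC0-240.** SAP Table 8.1 uses linear trapezoids. If the 240-minute value is missing, BLQ or not reportable, it is to be interpolated or extrapolated, and the parameter is dropped if that is unreliable.

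**The concern.** Adding Clast/Kel to AUCt is valid only if Clast is the concentration at the time where AUCt ends. As defined, the two can refer to different times, and the plan's own zeroing rule produces that case. The whole tail then vanishes. AUC%extrap, which should warn of heavy extrapolation, shows 0% for that profile. The reported area to infinity can also be smaller than the reported area to 240 minutes, which is impossible for one curve.

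AUCinf and Clast are named endpoints in both documents. A second analyst could not tell from Table 8.1 which Clast to put into the formula.

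The synopsis raises a related point. It ends the primary AUCt at the last time point measured, while the protocol abbreviations and SAP Table 8.1 end it at the last non-zero concentration.

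**Working it through.** The documents give no numerical PK result to reproduce, so the check applies their definitions to the stated sampling grid. Concentrations, C0 and half-lives below are assumptions unless a source is given.

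**1. When the 240-minute value becomes zero.** The baseline term is C0·exp(−Kel·t1), with the half-life fixed at 120 min and the pre-use sample at −5 min (SAP 8.3). At 240 min, t1 = 245, so the term is C0 × 2^(−245/120) = 0.243 × C0. The adjusted value is zero when the unadjusted value is at or below that: 0.49 ng/mL for C0 = 2, 0.97 for C0 = 4. Protocol 7.3.1 sets BLQ values to half the LLOQ before adjustment, so zeroing needs C0 of at least 0.5/0.243 = 2.06 times the LLOQ.

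**2. Algebra, last non-zero value at 120 min.**
- AUCinf, literal = AUCt + 0/Kel = AUCt, so AUC%extrap = 0.
- AUC0-240, with zero entered = AUCt + ½ × 120 × (C120 + 0) = AUCt + 60 × C120.
- Gap = 60 × C120: 6, 30, 60 and 120 ng·min/mL for C120 = 0.1, 0.5, 1 and 2 ng/mL.
- Lost tail = C120/Kel. For C120 = 1 it is 87, 130 and 173 ng·min/mL at fitted half-lives of 60, 90 and 120 min.

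Kel needs only three non-zero points (SAP Table 8.1), so it can still be fitted.

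**3. Worked profile.** Adjusted values 0, 4, 7, 9, 10, 9, 7, 4, 3, 2.4, 1.0, 0 ng/mL at 0, 2, 4, 6, 8, 10, 15, 30, 45, 60, 120, 240 min. Kel from the 45, 60 and 120 min points is 0.01463/min (half-life 47 min).

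| Quantity | ng·min/mL |
|---|---|
| AUCt (0–120) | 386.5 |
| AUCinf, literal Clast = 0 | 386.5 (0% extrapolated) |
| AUCinf, Clast = C120: 386.5 + 68.3 | 454.8 (15.0% extrapolated) |
| AUC0-240, zero entered | 446.5 |
| AUC0-240, C240 extrapolated to 0.173 | 456.9 |

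Literal AUCinf is below AUC0-240 on either route.

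**4. Does redefining Clast restore the ordering?** With zero entered, C120/Kel exceeds 60 × C120 only if the fitted half-life is above 60 × ln 2 = 41.6 min. With C240 extrapolated by Kel, the condition is 1/Kel > 60 × (1 + exp(−120 × Kel)), i.e. a half-life above about 49 min. At 49.3 min the two sides are 71.1 and 71.1. The worked profile, at 47 min, passes the first test (454.8 > 446.5) and narrowly fails the second (454.8 < 456.9).

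**5. Sensitivity to the assumed profile.** Nine assumed bi-exponential profiles (true half-life 50–75 min, C0 2–5 ng/mL) had their 240-minute value zeroed by the baseline formula itself. Their fitted half-lives were 14–35 min. Literal AUCinf was 0.4–13.6% below AUCt plus the matched tail, and 1.2–14.0% below AUC0-240 with zero entered. In all nine the matched AUCinf was still below AUC0-240. A mono-exponential decline with half-life 60–90 min and C240 simply set to zero gave losses of 26–40%.

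**6. AUCt under the synopsis end point.** For the worked profile AUCt would be 446.5 instead of 386.5, again 60 × C120. Literal AUCinf would then equal AUC0-240.

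**The case against.** The strongest reply is that the AUCinf row carries its own gloss, "is the last observed/measured concentration", directly below an AUCt row that ends at the last measurable non-zero value. A zero assigned to a negative difference is hardly observed or measured, so a competent analyst would use the matched value and the formula would be right. That reading is available. But the Clast row of the same table then means something else: the listed Clast would be 0 while a different, unlisted Clast sat inside AUCinf. The ambiguity remains.

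The objection that this is secondary also stands. SAP 8.6 models only Cmax and AUCt; AUCinf, AUC%extrap and Clast are listed and summarised.

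So does the objection on frequency. After at least 12 hours of abstinence, six half-lives at 2 hours, a C0 of 1–3 ng/mL implies 64–192 ng/mL when abstinence began. Zeroing needs decline faster than the fixed 2 hours, and fast eliminators tend to have the lowest C0. Simulations at Cmax 3 ng/mL gave zeroed shares of 4–24% under one set of assumed inputs and 0–0.7% when C0 was derived from each subject's half-life. The documents cannot decide between them.

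**Conclusion.** The definitions do not fit together. Taken literally, they give a wrong AUCinf and a misleading 0% extrapolation for any profile with a zeroed 240-minute value and an estimable Kel. With the last non-zero value at 120 minutes, the shortfall is C120/Kel against the matched AUCinf, and 60 × C120 against AUC0-240 if zero is entered. In the assumed profiles the loss against the matched AUCinf ran from under 1% to about 40%, so no single percentage should be quoted. The correction is worth making because the rule is wrong as written and costs almost nothing to repair.

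Four stronger inferences are not supported:
- **Bias against low-delivery sticks in the product comparison.** A lower late concentration does make a zero likelier for a given C0, but the frequency is unknown and AUCinf enters no planned comparison.
- **An error in T1/2.** It is ln 2/Kel, fitted on non-zero points; Clast does not enter.
- **A wrong primary analysis.** The analysed AUCt has the same end point in the protocol abbreviations and SAP Table 8.1. Only the synopsis differs, and it uses the same end point as Clast, so there are two competing end points, not three.
- **That redefining Clast guarantees AUCinf at or above AUC0-240.** It restores the tail. The ordering can still fail at short fitted half-lives, because a linear trapezoid across the 120-minute gap overstates a fast decline.

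**What to change.** 1. Define Clast once, in the protocol abbreviations, Protocol 7.3.1 and SAP Table 8.1, as the last non-zero baseline-adjusted concentration, at the time where AUCt ends. Use that value in AUCinf and AUC%extrap, and drop the separate gloss in the AUCinf row. If the 240-minute value is wanted, report it under its own name, such as C240.
2. Bring the synopsis objective and the undefined time t in Protocol 7.3.1 into line with the AUCt end point in SAP Table 8.1.
3. State whether an assigned zero at 240 minutes enters AUC0-240 as zero or falls under the BLQ interpolation/extrapolation rule. Add that AUCinf may still be below AUC0-240 when the fitted half-life is short (below about 42 min with zero entered, about 49 min with C240 extrapolated by Kel), and list any such profiles.

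The cost is a few lines of text in the protocol and SAP and a matching check of the PK software settings. No new data or samples are needed, and the SAP 8.6 models do not change.

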1. INTRODUCTION AND BACKGROUND

1.1 Background

Smoking is a cause of serious diseases in smokers, including lung cancer, heart disease and emphysema. Despite the well characterised health risks, smoking rates in adult populations worldwide remain at 15% to 25%. In addition to methods of helping people quit, investigations are ongoing into the health benefits of reducing exposure to toxicants in people who continue to use tobacco and nicotine, in the absence of combustion. This is being done through the development of new non-combustible tobacco and nicotine products, often referred to as next generation products (NGP).

Tobacco-related health risks are assumed to be due to repeated and sustained exposure to a range of smoke toxicants at high levels. Smoke from conventional cigarettes (CC) is a complex and dynamic mixture of more than 7000 chemical constituents, in both its particulate and vapour phases. Some of these chemicals have been identified as potential contributors to the harmful effects of cigarette smoke and can be evaluated by measuring the levels of these chemicals themselves, or their metabolites, in urine.

Nicotine is an addictive chemical present in combustible cigarette smoke. Nicotine is rapidly absorbed into the bloodstream during cigarette smoking, from where it is rapidly distributed causing both systemic and central effects. In the central nervous system, nicotine acts at neuronal nicotinic receptors and this interaction may underpin its effects on mood and relaxation. The pharmacokinetic (PK) profile of nicotine during cigarette smoking is a rapid rise and fall in plasma nicotine concentrations. Correspondingly, the delivery of nicotine to the brain, and the consequent pleasurable effects experienced by the smoker, are also rapid.

Imperial Brands PLC aim to increasingly transition adult smokers, who would otherwise continue to smoke, to NGPs that are potentially less harmful than CC. Heated tobacco (HT) and electronic cigarettes (E-cigarettes) are two platforms that are being increasingly recognised by public health bodies and regulators as having the potential to reduce the risk of continued smoking. HT products also offer greater optionality in parts of the world where vaping is not permitted or where smokers prefer HT. Imperial Brands have therefore added the Pulze heated tobacco product (HTP) device and iD stick HT consumables to a growing repertoire of NGP.

1.2 Pulze HT Previous Clinical Experience

No clinical studies have been conducted for the Pulze HT products. Pulze was commercially available following a city pilot launch in Fukuoka, Japan, in May 2019.

